### 3.1.6 Laboratory variables

The parameters haematology, serum chemistry, urinalysis (outlined in Table 5 in Section 5.2.9 of the clinical study protocol), and fasting lipid profile (high density lipoprotein cholesterol, low density lipoprotein cholesterol, and triglycerides) will be explored.

Glucose (serum chemistry), cholesterol (serum chemistry), high density lipoprotein cholesterol (fasting lipid profile), low density lipoprotein cholesterol (fasting lipid profile), and triglycerides (fasting lipid profile) will only be considered in tables and figures if the subject fasted for at least 8 hours prior to the assessment.

Laboratory data will be reported in SI units. Changes from baseline in haematology, clinical chemistry, and lipid profile variables will be calculated.

Absolute values will be compared to the reference range [REDACTED] and classified as low (below range), normal (within range or on limits), or high (above range). All values (absolute and change) falling outside the reference ranges will be flagged.

Treatment-emergent laboratory/vital signs changes will be defined for post-baseline values according to the reference ranges [REDACTED]

Urinalysis data will be categorised as negative (0), trace, positive (+), or strongly positive (++, +++, or >+++)) at each time-point. Treatment-emergent changes will also be assessed.

[figure not shown]
Treatment-emergent changes of urinalysis data are defined as

[figure not shown]
- Negative/Trace/+ at baseline to ++, +++, +++++ at any post-baseline value OR
- Increase from baseline of at least ++ at any post-baseline value.

[figure not shown]
For the liver function tests: aspartate transaminase (AST), alanine transaminase (ALT), alkaline phosphatase, gamma glutamyl transferase (GGT), and total bilirubin, the multiple of

the upper limit of the normal (ULN) range [REDACTED] will be calculated for each data point. Multiple = Value / ULN, ie, if the ALT value was 72 IU/L (ULN = 36) then the multiple would be 2. Subjects meeting both of the following biochemical criteria for Hy's law (potential Hy's Law) at any point during the study (not necessarily at the same time) will be flagged:

[figure not shown]
- AST  $\geq 3x$  ULN and/or ALT  $\geq 3x$  ULN
- Total bilirubin  $\geq 2x$ ULN

[figure not shown]

[figure not shown]

[figure not shown]

[figure not shown]

[figure not shown]

### **3.3 Assessment of study population**

#### **3.3.1 Demographic and baseline characteristic variables**

Demographic characteristics (including geographic region, age, gender, ethnicity, and race) and baseline characteristics (including height, weight, body mass index [BMI], and disease characteristics) from the Phase 3 feeder studies will be used.

#### **3.3.2 Medical history**

Medical histories will be coded using the latest MedDRA version. Medical history as recorded in the phase 3 feeder studies will be explored separately for past and current conditions as given in the eCRF.

#### **3.3.3 Prior and concomitant medications**

All medications will be coded using the latest version of World Health Organization Drug Dictionary (WHO-DD).

Any medications taken by the subject prior to the first dose date of investigational product in the phase 3 feeder studies will be considered prior medication. Any medication taken by the subject at any time between the date of the first dose (including the date of the first dose) of investigational product up to end of study/participation, inclusive, will be considered concomitant medication. Any medication started prior to the first dose of investigational product of the phase 3 feeder studies and ended/ was ongoing after the first dose up to end of study/participation will be considered as both prior and concomitant medication. In case of missing or partial dates, the imputation rules [REDACTED] will be applied to classify medication as prior and/or concomitant, as appropriate.

Disease related treatments at baseline and during the LTE study will be explored every 3 months (ie, at baseline and weeks 52, 64, 76, 88, 104, 116, 128, 140, 156, 168, 180, 192, and 208). Disease related treatments at a specific visit are defined as all medications with therapy reason containing “disease under study” with an intake at the date of the respective visit. For baseline and Week 52 visits, the timepoints as derived in the feeder studies will be used. For all other timepoints, the scheduled day will be used. If a subject discontinued in a visit window before the scheduled day, the date of discontinuation will be used instead. The medications will be presented in the following categories:

- **Anti-malarial**  
defined as medications with an ATC code level 4 of P01BA (aminoquinolones) and P01AX (Other agents against amoebiasis and other protozoal diseases)
  - Any anti-malarial
  - Anti-malarial only
  - Anti-malarial in combination with OCS and/or immunosuppressants
- **Azathioprine**  
defined as medications with a preferred term of azathioprine or azathioprine sodium
- **Methotrexate**  
defined as medications with a preferred term of methotrexate or methotrexate sodium
- **Mycophenolate**  
defined as medications with a preferred term of mycophenolate mofetil or mycophenolate sodium or mycophenolic acid
- **Mizoribine**  
defined as medications with a preferred term of mizoribine
- **OCS**
  - Any OCS
  - OCS only
  - OCS in combination with immunosuppressants and/or anti-malarial
  - Time on corticosteroids up to randomisation
- **NSAID**  
defined as medication with an ATC code level 4 of M01AB, M01AC, M01AE, M01AG, M01AH, or M01AX except preferred terms SULFASALAZINE, and RABBIT VACCINIA EXTRACT
- **Other SLE medication**  
defined as SLE medications not covered within the above categories

Starting with Week 52, the change of medication use versus baseline will be explored for each of the above medication categories as follows:

- **Added**  
defined as intake of at least 1 medication of the respective category at the respective visit but no intake of any medication in the respective category at baseline
- **No change**  
defined as either intake of at least 1 medication of the respective category at the respective visit and baseline or no intake of any medication in the respective category at the respective visit and baseline
- **Discontinued**  
defined as no intake of any medication of the respective category at the respective visit but intake of at least 1 medication in the respective category at baseline

### 3.3.4 Exposure of investigational product

An infusion of IP is defined as follows:

- Start time and end time of study drug infusion are not missing and start time and end time are not equal, and
- Volume of infusion bag prior to infusion start is greater than volume of infusion bag at the end of infusion or investigator confirmed that study drug was administered according to protocol.

The duration of exposure to the investigational product per subject is defined as the number of days between the start and the end dates of investigational product plus the dosing frequency time:

For the subjects randomised to Placebo in the feeder study who switch to Anifrolumab, the following definition applies, to account for exposure time of the feeder study (placebo) up until the day before their first dose of Anifrolumab in the LTE study:

Duration of exposure (days) = ([first dose date in LTE-1]) – first dosing date in feeder study + 1,

For the All Anifrolumab group the following definition applies, to account only for their exposure time of Anifrolumab:

Duration of exposure (days) = (Last Anifrolumab dosing date + 28 days) – first Anifrolumab dosing date + 1,

For all other subjects, duration of exposure is defined as:

Duration of exposure (days) = (Last dosing date + 28 days) – first dosing date + 1.

Duration of LTE exposure is consequently defined as

Duration of LTE exposure (days) = (Last dosing date of LTE study + 28 days) – first dosing date of LTE study + 1.

The total subject years of exposure is the sum of duration of exposure (days) of all subjects in the respective treatment group divided by 365.25 (days/year).

The total number of infusions and infusions during LTE will be counted per subject.

The time to discontinuation of investigational product is the same as the duration of exposure.

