#### **7.2.6 Documentation of investigational product administration**

Both the duration of the investigational product infusion and the duration of investigational product administration will be recorded. The duration of investigational product infusion and duration of investigational product administration will be calculated as follows:

- Duration of infusion: the amount of time elapsed from the infusion start time to the infusion stop time. Infusion start time is defined as the time point where investigational product is first infused into the subject. Infusion stop time is defined as the time point where the infusion pump completes infusion of the investigational product, not including the saline flush.

For example: an infusion with a start time of 12:00 PM would have a duration of infusion recorded as 30 minutes (a time between 12:00 PM and 12:30 PM).

- Duration of administration: the amount of time elapsed from the infusion pump start time to the infusion pump stop time PLUS the time required to complete the additional flush of saline. The duration of administration will always be greater than the duration of infusion and will always include the additional flush of saline.

Initial IV bag compatibility studies demonstrate that anifrolumab is compatible with IV bags composed of polyolefin that is latex-free, polyvinyl chloride (PVC)-free, and diethylhexyl phthalate (DEHP)-free, and IV administration lines composed of PVC and polyethylene that are latex-free and DEHP-free. Additional studies demonstrate that anifrolumab is compatible with IV bags and ancillaries comprising materials as described in [Table 6](#) and [Table 7](#).

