#### **2.1.2 Full analysis set – LTE Study**

The full analysis set – LTE Study will consist of all subjects who were randomised and received at least 1 dose of investigational product in the LTE Study. Subjects will be analysed according to the Intention-To-Treat principle (i.e., as randomised). Subjects who withdraw consent to participate in the study will be included up to the date of their study termination.

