### 3.1.1 Adverse events

Adverse events experienced by the subjects will be collected throughout the entire studies and will be coded using the latest version of Medical Dictionary for Regulatory Activities (MedDRA).

Adverse event data will be categorised according to their onset date based on the last dose of administration in either the feeder studies or the LTE, whichever is later, as follows:

In general:

- AEs occurring during treatment:  
An AE during treatment is defined as an AE with a date of onset  $\geq$  day of first dose of investigational product and  $\leq$  date of last dose of investigational product + 28 days.
- AEs occurring during follow-up:  
An AE during follow-up is defined as an AE with a date of onset  $>$  date of last dose of investigational product + 28 days and  $\leq$  date of last dose of investigational product + 84 days.
- AEs occurring during treatment and follow-up:  
An AE during treatment and follow-up is defined as an AE with a date of onset  $\geq$  day of first dose of investigational product and  $\leq$  date of last dose of investigational product + 84 days

The following are exceptions:

- For subjects in the “Randomised Placebo” treatment group with a switch to anifrolumab 300 mg in the LTE study, AEs with a date of onset  $\geq$  day of first dose of investigational product in the LTE study will not be considered in the categories above, except for those with an onset on the day of first dose of investigational product in the LTE that are recorded in the Phase 3 feeder studies.
- For subjects in the “All Anifrolumab” treatment group who were randomised to placebo in the Phase 3 feeder studies, AEs with a date of onset  $<$  day of first dose of investigational product in the LTE study and those with an onset on the day of first dose of investigational product in the LTE that are recorded in the Phase 3 feeder studies will not be considered in the categories above.

In general, an AE during LTE is defined as an AE in the categories above with a date of onset  $\geq$  day of first dose of investigational product in the LTE study. AEs with onset on the day of first dose of investigational product in the LTE, but which were recorded in the Phase 3 feeder studies will not be considered as occurring during the LTE.

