The event rate per 100 subject years including 95% CIs will be summarised for the following categories. Summaries of AESIs will be presented by AESI category (non-opportunistic serious infections, opportunistic infections, anaphylaxis, malignancy, herpes zoster, tuberculosis, influenza, vasculitis [non SLE], and major acute cardiovascular events) and preferred term. Summaries for SAEs will be presented by MedDRA system organ class and preferred term.

- Any AESI
- Any AESI by time interval for the first onset of event – alternative event rates
- Any AE leading to discontinuation of IP by time interval for the first onset of event – alternative event rates (combined feeder & LTE study, by preferred term)
- Any AESI – alternative event rates
- Any SAE (including events with outcome = death) (during treatment and during follow-up separately. No event rate for during follow-up will be presented)
- Any SAE (including events with outcome = death) by time interval for the first onset of event – alternative event rates

The event rate per 100 subject years will be summarised by MedDRA system organ class and preferred term for the following AE categories.

- Any AE (during treatment and during follow-up separately. No event rate for during follow-up will be presented)
- Any AE by descending preferred term (during treatment, and during the LTE treatment)
- Any AE with outcome = death
- Any SAE by descending preferred term (including events with outcome = death) (during treatment, and during the LTE treatment)
- Any AE leading to discontinuation of investigational product
- Any AE by relationship to investigational product (yes, no) (multiple occurrences of an AE in 1 subjects will only be counted once as related if at least one AE is related and as not related if all occurrences are not related)
- Any AE by maximum intensity (mild, moderate, severe) (i.e., multiple occurrences of an AE in 1 subjects will only be counted once with the maximum intensity in this AE)
- Any other significant AE

The alternative event rate per 100 subject years will be summarised by MedDRA preferred term for the following AE categories.

- Any COVID-19 related AE (for the LTE Study only, only subjects remaining in the study on 11-Mar-2020 will be included)
- Any SAE prior to the COVID-19 pandemic (for the LTE Study only)
- Any SAE during the COVID-19 pandemic (for the LTE Study only, only subjects remaining in the study on 11-Mar-2020 will be included)

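### SAP 3.3.4 does not count a dose that was demonstrably given if one of its clock times is missing, and the SAP does not say whether first-dose, last-dose and switch dates follow the same rule

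*SAP*

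**What the plan says.** SAP 3.3.4 (Exposure of investigational product) defines an infusion by two conditions joined by a logical and:

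- First: "Start time and end time of study drug infusion are not missing and start time and end time are not equal".
- Second: the bag was fuller before the infusion than after it, or "investigator confirmed that study drug was administered according to protocol".

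The same section uses the term for counting: "The total number of infusions and infusions during LTE will be counted per subject". SAP 4.2.3.3 uses it for the infusion/no-infusion tables by visit. It also uses it for dates in the Kaplan-Meier plot of discontinuation: last placebo infusion as censoring date for switchers in Randomised Placebo, first LTE infusion as the start for switchers in All Anifrolumab, and last infusion as censoring date in interim analyses.

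The adverse event rules use different words. SAP 3.1.1 sets its windows from the first and last dose (plus 28 or 84 days), and its exception "For subjects in the “Randomised Placebo” treatment group with a switch to anifrolumab 300 mg in the LTE study" cuts at the first LTE dose. SAP 2.1.2 admits to the LTE analysis set those who "received at least 1 dose of investigational product in the LTE Study". The visible text does not define a dose separately, and it does not say that dose dates come from the 3.3.4 definition.

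Protocol 7.2.6 requires infusion duration to be recorded and gives this definition: "Infusion stop time is defined as the time point where the infusion pump completes infusion of the investigational product".

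**The concern.** The investigator's confirmation sits only in the second condition. It cannot rescue a record that fails the first, so the strongest evidence that drug was given is overruled by a blank clock field. In a study whose primary outcome is safety rates, a rule on exposure should not discard doses known to have been given.

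The first and last dose dates also fix the adverse event windows, the person-time, the boundary between Year 1 and Year 2, and the day on which a placebo switcher leaves Randomised Placebo and enters All Anifrolumab. If those dates are derived from the infusion definition, an incomplete time record can move events between periods. In one specific case it moves them from anifrolumab to placebo, which would understate harm on anifrolumab.

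**Working it through.** **1. The rule.** Let A = both times present and different, B = bag volume fell, C = investigator confirmed. SAP 3.3.4 reads: infusion = A and (B or C).

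| Record | A | B or C | Counted |
|---|---|---|---|
| Both times entered, volume fell | yes | yes | yes |
| Stopped early, both times entered, volume fell | yes | yes | yes |
| Volume fell and investigator confirmed, one time blank | no | yes | **no** |
| Both times entered, no volume fall, no confirmation | yes | no | no |

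The third row is the defect. The fourth row is a safeguard worth keeping. No fallback for missing times is visible. A redacted appendix deals with partial or missing dates, and its title does not mention clock times.

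**2. Effects that need no assumption.** Each uncounted dose lowers the subject's infusion count by 1 and appears as no infusion at that visit. If it is the first LTE or last infusion, it can also shift the start or censoring date in the Kaplan-Meier plot.

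**3. Effects if dose dates follow the definition.** No figure in the plan depends on the rule, so there is none to reproduce. The schedule figure agrees: 152/4 + 1 = 39 LTE doses.

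*First LTE infusion uncounted, placebo-to-anifrolumab switcher.* The Week 48 feeder dose is Day 48 × 7 + 1 = 337. The first LTE dose is nominally Day 365 and the next is Day 365 + 28 = 393. Onsets on Days 365 to 392 then precede the derived switch. They leave All Anifrolumab and fall in Randomised Placebo, inside even a window counted from the last feeder dose (337 + 84 = Day 421). Person-time moved is 28/365.25 = 0.077 subject-years. LTE Day 1 has no visit window and the next visit has ±7 days, so the range is 21 to 35 days, or 0.057 to 0.096 subject-years. In any subject, these events also move from Year 2 to Year 1 and out of the LTE-only summaries. A subject with no other LTE infusion would leave the LTE analysis set.

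*Last infusion uncounted.* Days are counted from the true last dose, and the derived last dose is one spacing earlier. An onset counts as treatment up to last dose + 28 and as follow-up up to last dose + 84, both inclusive.

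| Spacing (days) | Treatment becomes follow-up | Follow-up drops out |
|---|---|---|
| 14 | +15 to +28 | +71 to +84 |
| 21 | +8 to +28 | +64 to +84 |
| 28 | +1 to +28 | +57 to +84 |
| 35 | 0 to +28 | +50 to +84 |
| 42 | 0 to +28 | +43 to +84 |

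At 28-day spacing, 28/84 = one third of the 84-day window is lost.

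*Middle infusion uncounted.* No first-dose or last-dose window moves. A reaction on that day goes to the preceding visit in the by-visit analysis of reactions in SAP 3.1.1.

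**4. Scale.** With about 575 subjects at about 4:1 (SAP 1.2), LTE placebo is about 575/5 = 115. Feeder placebo subjects are re-randomised 1:1, so switchers are also about 115. The rate of missing times is not given. As an assumption, 0.1% gives 115 × 0.001 = 0.1 and 1% gives 115 × 0.01 = 1.2 affected first LTE infusions. One misplaced event adds 1000/517 = 1.93 per 1000 subject-years to Randomised Placebo and removes 1000/1343 = 0.74 per 1000 from All Anifrolumab, using the planned follow-up in SAP 1.3.

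**The case against.** **The link to adverse events is not written down.** SAP 3.1.1 and 2.1.2 speak of dose or administration, and 3.3.4 itself uses infusion for counts but dosing dates for duration. The amendment history places the adverse event categories in version 2.0 (2019) and the infusion definition in version 5.0 (2022), so the windows were specified before the rule existed. This stands, and a reader who infers that the SAP does misassign events to the wrong arm goes beyond the text. The inference is still plausible. No other definition of a dose is visible. SAP 3.3.4 equates time to discontinuation with duration of exposure, which is built from dosing dates, while 4.2.3.3 describes the same variable in terms of infusions.

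**Missing times should be rare.** Protocol 7.2.6 requires durations to be recorded and Protocol 9.4 has missing data queried. This stands and limits the frequency.

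**Infusions stopped for a reaction.** A reader might infer that these are the doses lost. The documents do not support that: such an infusion counts once both times are entered and the volume fell. What remains is that the protocol ties stop time to the pump completing, so the time to enter for an aborted infusion is left unclear.

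**Serious events after the last dose.** The during-treatment SAE table has a follow-up counterpart without a rate ("No event rate for during follow-up will be presented"), so a reader might infer that displaced events vanish. SAP 4.2.1.1 bases its summaries on treatment and follow-up together, so events on days +1 to +28 stay in the main rates. At 28-day spacing, a reaction on the infusion day itself also stays on treatment. Only events on days +57 to +84 would be lost.

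**Conclusion.** The rule as written gives a wrong result for a dose shown to have been given but lacking a clock time, and no visible text overrides it. The effect on infusion counts, the by-visit infusion tables and the infusion dates in the discontinuation plot is certain in kind.

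The effect on adverse event periods and arms is conditional on dose dates following 3.3.4. An arm shift then needs one specific case: the first LTE infusion of a placebo-to-anifrolumab switcher, with an event in that cycle. At an assumed 0.1% to 1% missing, about 0.1 to 1.2 switchers would be affected, before asking whether they had an event. A single such event would still be visible against the SAP's rare-event illustration of 1 per 1000 subject-years.

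A reader might apply the same assumed rates to all 575 × 39 = 22,425 planned LTE doses and infer 22 to 224 affected doses. That is not a measure of misplaced events: it ignores dropout, and most of those are middle doses that move no first-dose or last-dose window. The point is a worthwhile correction to a definition and does not threaten the main results.

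**What to change.** In SAP 3.3.4:

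- Count an infusion if the bag volume fell or the investigator confirmed administration, whether or not both clock times are complete.
- State that first-dose, last-dose and switch dates, wherever the SAP uses them, are the administration dates of any such infusion.
- Keep the condition of complete and different times for calculating infusion duration only.
- Do not make complete and different times sufficient alone. That would count a record with no fall in volume and no confirmation, and so remove a safeguard that the current rule has.

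The cost is a rewording of the definition, a sentence on dose dates and one derivation change. The downside is that a few doses with incomplete time records are counted as exposure.
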